2.8 Handling Missing Data

In general, missing data will not be imputed and analysis is restricted on available data, with the following exceptions:

- For time-to-event endpoints (DFS, OS), incomplete dates will be handled as described in Section 5.2.
- Response rates will consider missing response assessments as described in Section 5.2.
- Missing causality assessment for adverse events will lead to handling of the AE as related (see Section 7.3 . of the CSP)

2.9 **Protocol Deviations**

Potential protocol deviations will be collected prior to database snapshot for the main analysis. Potential protocol deviations will be discussed in a data review meeting (DRM) prior to database snapshot for the main analysis and will be classified as relevant or not relevant. A protocol deviation will be considered relevant if it has a potential influence on the efficacy analysis. Relevant protocol deviations will lead to exclusion from the PP Population. Relevant protocol deviations can be one of the following but are not limited to:

- at least one of the major inclusion criteria was not met (criteria with relevant impact on efficacy)
- at least one of the major exclusion criteria was fulfilled (criteria with relevant impact on efficacy) •
- administration of prohibited therapies during the screening and treatment phase as defined in the CSP •
- administration of no study treatment •
- no documentation of tumor assessment after start of study treatment •
- erroneous dose of study medication .

Medical Coding 2.10

All information regarding the medical coding of medical history and adverse events can be found in the coding guideline.

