2.11 Analysis Populations

2.11.1 Intent-to-Treat population

The Intent-to-Treat (ITT) Population includes all enrolled. A patient is regarded as enrolled if considered eligible for treatment start at screening (i.e. eCRF question "Have all screening assessments been performed and is patient considered eligible for treatment start" is answered with yes by the investigator).

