2.11.2 Per-Protocol population

The Per-Protocol (PP) Population will comprise all patients of the ITT population who had no protocol deviation relevant for efficacy evaluation. PP Population will be defined in the DRM performed before the main analysis. For definition of relevant protocol deviations, see Section 2.9.

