2.11.3 Safety population

The safety population consists of all patients who received at least one dose of study medication.

If the Safety and ITT Population are identical (i.e. all enrolled patients received at least one dose of treatment medication) the analysis will be performed for the Safety Population and the ITT Population together, labelled with "Safety/ITT Population".

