5.2 Definitions

- Disease-free survival (DFS) will be defined as the time length from the date of surgery to the date of tumor recurrence or death (tumor recurrence as reported on follow-up pages in the eCRF, death as reported in the end of study page in the eCRF). Patients that had no tumor recurrence and did not die will be censored at the date of last contact when patient was alive (as reported on the end of study page in the eCRF).
- Overall survival (OS) will be calculated as the time length from the date of surgery to the date of death. Patients that did not die will be censored at the date of last contact when patient was alive (as reported on the end of study page in the eCRF).
- For both DFS and OS the following rule will be applied for incomplete dates: The date of surgery is assumed to always be completely known (day, month and year available), otherwise DFS and OS will not be calculated. For the end dates (death, tumor recurrence, last date patient was alive) patients will be secured at the earliest possible date. E.g. if the date of death is "UK/05/2019" then the patient is censored at 01/05/2019 and thus being considered event-free until this date and status is considered unknown after

this date. If this rule results in negative survival time, the patient is not considered for Kaplan-Meier analysis.

• Δ tumor size will be defined as the difference [mm] between "current SUM LD" and "baseline sum LD" on the tumor response assessment page of the eCRF.

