7.1.3 Efficacy Analysis

| No | Legend | Content |
|--------|--------------------------------------|----------------------------------|
| 14.3.1 | Tumor Response at Pre-Surgery Visit | Overall response |
| | (PP Population) | Δ tumor size |
| 14.3.2 | Tumor Regression Grading Stage (PP | |
| | Population) | |
| 14.3.3 | Kaplan-Meier Statistics for Disease- | |
| | Free Survival (PP Population) | |
| 14.3.4 | Kaplan-Meier Statistics for Overall | |
| | Survival (PP Population) | |
| 14.3.5 | Tumor Staging (PP Population) | Tumor stage |
| 14.3.6 | Tumor Marker Values Over Time (PP | CEA |
| | Population) | Cyfra 21-1 |
| 14.3.7 | Tumor Marker Value's Change from | CEA |
| | Baseline (PP Population) | Cyfra 21-1 |

Confidential and intellectual property of Assign DMB. No part of this document or its contents may be duplicated, referenced, published or otherwise disclosed in any form or by any means without prior written consent of Assign DMB.

Page 19 of 23

| 14.3.8 | Lung function test results (PP | VC MAX |
|-----------|--|---------------|
| | Population) | FVC |
| | | VC IN |
| | | • FEV1 |
| | | FEV 1% VC MAX |
| | | DLCO SB |
| | | DLCO/VA |
| | | DLCOc SB |
| | | DLCOc/VA |
| | | • pC02 |
| | | • pO2 |
| 14.3.9-16 | Tables 14.3.1-8 will be repeated for the ITT Population. | |

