| 16.2.4.16 | Surgeries performed (Safety Population) | Patient ID, Surgery performed, Date of surgery, |
| | | Method, Approach, Extensions, Systematic lymph |
| | | node dissection performed, Intraoperative blood |
| | | loss [m]], Intraoperative blood transfusion |

| | | performed, Post-operative complications, Length |
|-----------|---|---|
| | | of ICU stay, Re-admission to ICU, Date of re- |
| | | admisson |
| 16.2.4.17 | Vital signs (Safety Population) | Patient ID, Visit, Parameter, Value, Unit |
| 16.2.4.18 | Cardiac evaluation (Safety Population) | Patient ID, Visit, Evaluation performed, Cardiac |
| | | evaluation, Date, Result, Specification of |
| | | abnormality |
| 16.2.4.19 | ECOG performance status (Safety Population) | Patient ID, Visit, Date ECOG Score, ECOG Score |
| 16.2.4.20 | Routine Chest X-Ray (Safety Population) | Patient ID, Visit, Chest X-Ray performed, Date of |
| | | performance, Tumor visible, Comments |
| 16.2.4.21 | Pregnancy test (Safety Population) | Patient ID, Visit, Pregnancy test performed, Date |
| | | of test, Reason not performed, Method, Result |
| 16.2.4.22 | Quality of Life (Safety Population) | Patient ID, Visit, Date of assessment, Quality of |
| | | Life question, Answer/Result |

Page 23 of 23

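### Overall survival is timed from surgery, so the OS table labelled ITT leaves out enrolled patients who never have surgery

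*SAP*

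**What the plan says.** SAP 5.2 defines the endpoint: "Overall survival (OS) will be calculated as the time length from the date of surgery to the date of death". Patients who have not died are censored at the last contact when alive. The same section deals with dates: "The date of surgery is assumed to always be completely known (day, month and year available), otherwise DFS and OS will not be calculated". DFS has the same origin.

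SAP 2.11.1 takes all enrolled patients as ITT and fixes enrolment before treatment: "A patient is regarded as enrolled if considered eligible for treatment start at screening". SAP 5 runs efficacy primarily on PP and repeats it on ITT. In SAP 7.1.3 the OS table is 14.3.4, and "Tables 14.3.1-8 will be repeated for the ITT Population"; by position the ITT version is Table 14.3.12.

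The protocol sets no origin for OS; section 8.4.3 asks only for Kaplan-Meier curves. Its secondary objective (2.2) is the effect of neoadjuvant pembrolizumab on disease-free and overall survival.

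**The concern.** A survival curve that starts at surgery describes survival given that surgery was reached. A reader of an OS table labelled ITT will take it as survival of everyone enrolled. The patients left out are those who died, progressed or became inoperable before surgery, and their outcome is part of what a neoadjuvant strategy does to survival.

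The protocol foresees such patients. Section 1.4 names loss of resectability during the delay as the general risk of the approach. Section 3.1 sends patients with progression or intolerable toxicity during immunotherapy to an end-of-treatment visit and then to follow-up. Section 5.4 makes failure to undergo surgery as planned an interim stopping criterion. Sections 3.4 and 5.2.6 follow all enrolled patients for survival, so the trial collects the data that the OS table then omits.

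**Working it through.** **Who is in the table**

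1. ITT membership is decided at the end of screening (SAP 2.11.1).
2. An OS value needs a complete surgery date (SAP 5.2). The sentence stands in the rule for incomplete dates and does not mention patients without surgery. That makes no difference: with no operation there is no start date and no fallback.
3. The ITT OS table therefore holds ITT patients with a surgery date. The condition is an operation, not a resection: listing 16.2.4.16 records "Patient ID, Surgery performed, Date of surgery", so a patient operated on but not resected still counts.
4. In PP the mismatch is conditional. SAP 2.9 does not list absence of surgery as a relevant deviation, but its list is open ("Relevant protocol deviations can be one of the following but are not limited to"), and "PP Population will be defined in the DRM performed before the main analysis". The mismatch arises only if that meeting keeps a never-operated patient.

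**How many patients**

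The plan's own binomial statement for N=30 reproduces: 1 − (1 − 0.095)^30 = 0.950. On the same model, an assumed no-surgery rate of 5% gives 1 − 0.95^30 = 78.5% probability of omitting at least one patient; 10% gives 95.8%. The documents set no upper bound. If the 80% feasibility criterion (protocol 8.1) is met, at most 6 of 30 lack surgery; this is an extreme, because delayed operations also count as failures and do have a date. The 3/15 rule (protocol 5.4) applies only at the interim.

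**How large the gap**

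Inputs from the documents:
- Discharge is at Day 60-74 (protocol schedule of assessments), about 2 weeks after surgery (protocol 3.2: 6 weeks after surgery is about 4 weeks after discharge). Surgery is then near Day 46-60, which is 45-59 days or about 1.5-2.0 months after first dose.
- Screening adds up to 28 days (protocol 5), with a 31-day limit from screening to treatment start (protocol 5.3), so surgery is about 1.5-3.0 months after consent.

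Assumptions not in the documents: 24-month OS of 85% from surgery in operated patients, with constant hazard; 24-month OS of 40-60% from the ITT origin in the others.

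Let d be the months from the ITT origin to surgery, q the unoperated fraction and Sn their 24-month OS. Operated patients are alive at surgery, so their 24-month OS from the ITT origin is So = 0.85^((24 − d)/24):
- d = 1.5: 0.8587
- d = 2.0: 0.8616
- d = 3.0: 0.8674

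All-enrolled OS is S = (1 − q)·So + q·Sn, and the gap is 0.85 − S. Example with q = 3/30, d = 1.5, Sn = 0.40: S = 0.9 × 0.8587 + 0.1 × 0.40 = 0.8128, gap 3.7 points.

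| Unoperated of 30 | Gap against OS from first dose (points) | Gap against OS from consent (points) |
|---|---|---|
| 0 | −0.9 to −1.2 | −0.9 to −1.7 |
| 1 | −0.3 to +0.7 | −0.9 to +0.7 |
| 3 | +1.5 to +3.7 | +0.9 to +3.7 |
| 4 | +2.3 to +5.3 | +1.8 to +5.3 |
| 6 | +4.1 to +8.3 | +3.6 to +8.3 |

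A positive gap means the SAP figure is too high. Two effects oppose each other: starting the clock later lowers 24-month OS, and dropping unoperated patients raises it. They cancel at 30·(So − 0.85)/(So − Sn) patients: 0.6 (d = 1.5, Sn = 0.40) to 1.3 (d = 2.0, Sn = 0.60) from first dose, and up to 2.0 (d = 3.0, Sn = 0.60) from consent.

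Sampling error, 1.96·√(0.85 × 0.15/n), is 12.8 points for n = 30, 13.5 for n = 27 and 14.3 for n = 24.

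**The case against.** The table at issue repeats, for ITT, a secondary and untested endpoint whose lead analysis is on PP. SAP 2.8 restricts analyses to available data, so a table named for a population but holding only patients with data is this SAP's habit; regression grading, also repeated for ITT, needs resected tissue too. The origin is stated openly and breaches no protocol rule. With 30 patients, death and last-contact dates (listing 16.2.1.3), survival status (16.2.3.11) and surgery performed (16.2.4.16) show each unoperated patient individually. Finally, the upward direction depends on the assumed 40-60%. With 70% survival in unoperated patients, a consent origin and d = 3.0, the effects cancel at 3.1 patients, and 3 of 30 gives a gap of −0.07 points.

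The last point stands: the statement that the bias runs upward from about 2 patients holds only within the assumed 40-60%. The limited role of the endpoint also stands, and it restrains the severity. The rest does not remove the defect. These patients' survival data are available; the choice of origin is what excludes them. The listings, the patient overview in Table 14.1.1 and the empty OS values in listing 16.2.3.6 let a careful reader find them, but do not put them into the estimate or its confidence limits.

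**Conclusion.** The concern holds. As written, the SAP produces an OS table labelled ITT that contains only patients with a surgery date. This is a population and labelling error in the SAP, not a breach of the protocol. For DFS, surgery is a legitimate origin and only the population label is wrong.

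The size cannot be fixed from the documents. On the stated assumptions the net gap is within 1 point with one unoperated patient and reaches 8.3 points at 6 of 30. Every gap is below sampling error. The trial is single-arm and descriptive, so what is at stake is a correctly populated all-enrolled estimate, not a comparative effect. It should be fixed before the analysis.

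**What to change.** - Time ITT OS from one origin that every ITT patient has, such as the informed consent date (listing 16.2.1.1). If every ITT patient was dosed, so that the Safety and ITT populations coincide (SAP 2.11.3), first dose (listing 16.2.4.1) can serve instead. Do not mix origins in one curve.
- With a consent origin, state that ITT status is set at the end of screening, so each curve begins with a short period, up to about 28 days, that is event-free by definition.
- Keep DFS and, if wanted, a second OS curve from surgery. Label them *patients with surgery*, give the number without surgery and the reasons, and do not present them as the full ITT or PP population.
- State in SAP 2.9 how patients without surgery are classified for PP, and time PP OS from the same origin as ITT OS.

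The cost is SAP wording and one or two extra Kaplan-Meier tables. All dates needed are already listed: consent, dose start, surgery, death and last contact. The ITT estimate may become less favourable, or slightly more favourable if nearly all patients have surgery. A consent origin lengthens every survival time by the screening and treatment period, so that curve cannot be read side by side with the surgery-based one.

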2. GENERAL CONSIDERATIONS

2.1 Conduct of Analysis

Two analyses will be performed for this study.

- Main analysis will be performed after all patients had their end of treatment, data entry for all visits except the follow-up visits is complete, data were cleaned, a Data Review Meeting was performed and database snapshot has been completed.
- Addendum analysis will be performed after last patient completed the entire study, follow-up data entry and cleaning are complete and database was closed.

Main analysis will summarize all data recorded up to the time of the database snapshot. Addendum analysis will only present data captured during follow-up. This means, the addendum analysis may only include overall survival, end of study details and subsequent cancer therapy. An SAE listing will also be prepared to show possible follow-up information of SAEs ongoing after end of treatment.

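### SAP 5.2 turns a known death with an incomplete date into a censored observation, and probably treats an incompletely dated recurrence the same way

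*SAP*

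**What the plan says.** SAP 5.2 starts both clocks at surgery. OS ends at death. DFS ends at recurrence or death. Ordinary censoring is kept for patients without the event. For OS: "Patients that did not die will be censored at the date of last contact when patient was alive". For DFS: "Patients that had no tumor recurrence and did not die will be censored at the date of last contact when patient was alive".

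A further rule in the same section, stated for both endpoints, covers incomplete dates: "For the end dates (death, tumor recurrence, last date patient was alive) patients will be secured at the earliest possible date". The worked example is a death in May 2019 with the day unknown: "then the patient is censored at 01/05/2019 and thus being considered event-free until this date and status is considered unknown after" it. The rule closes with an exclusion: "If this rule results in negative survival time, the patient is not considered for Kaplan-Meier analysis".

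No other section restores the event. SAP 2.8 only points back: "For time-to-event endpoints (DFS, OS), incomplete dates will be handled as described in Section 5.2". SAP 5.3 asks for Kaplan-Meier medians and rates at times such as 12, 24 and 36 months with 95% limits. SAP 2.14, which lists changes from the protocol, is silent on the rule, and Protocol 8.4.3 leaves the detail to the SAP.

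**The concern.** In the example the status after 1 May 2019 is not unknown. The patient died in that month, and only the day is missing. The rule therefore changes the event indicator as well as the date, and so conflicts with the two definitions above it.

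Kaplan-Meier estimation needs censoring that carries no information about the outcome. Here the event itself triggers the censoring. The closing exclusion adds a second loss: an event in the calendar month of surgery with the day unknown can give a negative time, and the patient then leaves the analysis altogether. These are the earliest postoperative events. DFS and OS are the only secondary endpoints, and the trial has no control arm in which a similar error might offset this one.

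**Working it through.** The plan gives no figure for this rule, so there is none to reproduce. The check is textual first, then a size illustration.

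**1. Which events are lost**

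| Situation | OS | DFS |
|---|---|---|
| Death incompletely dated, no earlier recurrence | lost | lost |
| Death incompletely dated, after a fully dated recurrence | lost | unaffected (the recurrence is the event) |
| Recurrence incompletely dated | unaffected | probably censored (inference) |

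The last entry is an inference. The operative sentence says *secured*, apparently a slip for *censored*, and the example is a death. Recurrence stands in the same list and the rule covers both endpoints, so censoring is the likely reading. The SAP does not say whether a later, fully dated death would then count as the DFS event. If it did, the event would be delayed rather than lost.

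**2. Direction**

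Take one event moved to censoring at the earliest possible date. Before that date nothing changes. Between that date and the true date the risk set is one too small, so the curve can be slightly low. From the true date onward the estimate is equal or too high.

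**3. Negative time**

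Surgery on 10 May and an event recorded as UK/05 of the same year: 1 May minus 10 May = -9 days. The patient is dropped.

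**4. Size of one lost event by 24 months**

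Inputs: n = 30 is the target sample size (Protocol 8.2). n = 24 is 80% of 30, the feasibility threshold in Protocol 8.1, used because both clocks start at surgery. The event counts k are assumed, and so is the absence of other censoring before 24 months.

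- All events kept: (n - k)/n
- First event lost: (n - k)/(n - 1)
- Last event lost: (n - k + 1)/n
- Standard error: sqrt(p(1 - p)/n), with p the all-kept value

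| Endpoint | n | k | All kept | First lost | Last lost | Shift (points) |
|---|---|---|---|---|---|---|
| DFS | 30 | 8 | 22/30 = 73.3% | 22/29 = 75.9% | 23/30 = 76.7% | +2.5 to +3.3 |
| DFS | 24 | 6 | 18/24 = 75.0% | 18/23 = 78.3% | 19/24 = 79.2% | +3.3 to +4.2 |
| OS | 30 | 3 | 27/30 = 90.0% | 27/29 = 93.1% | 28/30 = 93.3% | +3.1 to +3.3 |
| OS | 30 | 6 | 24/30 = 80.0% | 24/29 = 82.8% | 25/30 = 83.3% | +2.8 to +3.3 |
| OS | 30 | 9 | 21/30 = 70.0% | 21/29 = 72.4% | 22/30 = 73.3% | +2.4 to +3.3 |

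Standard errors for the DFS rows: sqrt(0.733 × 0.267/30) = 8.1 points and sqrt(0.75 × 0.25/24) = 8.8 points. The largest shifts are 3.3/8.1 = 0.41 and 4.2/8.8 = 0.48 of a standard error.

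If the event is kept and only its date moves earlier, the estimate stays (n - k)/n, provided the imputed date does not cross the 24-month point.

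**5. Several lost events (illustration only)**

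The 52% five-year relapse rate in Protocol 1.3, read as a constant DFS hazard, gives S(24) = 0.48^(24/60) = 74.6%. Losing a share f of events gives S^(1 - f): 76.8% for f = 10%, 79.1% for 20% and 81.4% for 30%. The shares are assumptions. The 52% is an overall relapse rate after curative-intent surgery; it is not specific to stage II/IIIA and is not recurrence-or-death.

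**The case against.** The strongest reply is that this may never matter. The trial has one centre and 30 patients, with three-monthly follow-up, source verification and site queries (Protocol 10). If every event date is complete, the rule does nothing. DFS and OS are secondary and descriptive, SAP 5.3 plans no tests, and in the two DFS cases one lost event moves the estimate by less than half a standard error. A reader could also find each case by comparing the death dates in listing 16.2.1.3 with the censoring flags in listing 16.2.3.6. All of this stands and limits the weight of the point. It does not justify the rule. The error runs one way at later time points and is avoidable, and the SAP itself provides for incomplete dates. The listings do not correct the Kaplan-Meier tables, and under Protocol 7.2.2 deaths from progression may not appear in the safety tables.

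It may also be said that the earliest possible date is conservative. That holds only if the event is kept.

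Two stronger readings are tempting, and the documents do not support them. One is that the SAP definitely removes every incompletely dated recurrence from DFS; the wording leaves this to inference, as shown above. The other is that the reported 24-month DFS will be inflated by several points. The share of incomplete dates is unknown, and a mature DFS analysis is not clearly planned. The main analysis follows the last end-of-treatment visit, before follow-up entry is complete: "Main analysis will summarize all data recorded up to the time of the database snapshot". At study end, "the addendum analysis may only include overall survival, end of study details and subsequent cancer therapy", which does not name DFS.

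**Conclusion.** The point holds for deaths on the explicit text: a known death with an incomplete date is censored, contrary to the section's own definitions. For recurrence it is the likely reading and needs clarifying. One lost event by 24 months raises the estimate by about 2.4 to 3.3 points with 30 patients (3, 6, 8 or 9 events) and by 3.3 to 4.2 points with 24 patients (6 events). These figures assume the stated event counts and no other censoring; with complete dates the effect is zero. The 10 to 30% scenarios only illustrate how losses add up and do not predict this trial's result. The primary endpoints, the feasibility criterion and the stopping rule are untouched. The rule should be fixed because it is wrong as written and cheap to correct.

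**What to change.** Amend SAP 5.2 as follows:

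- A known death or recurrence with an incomplete date remains an event; only its date is imputed.
- Use one imputed death date for both OS and DFS: the earliest possible date, but not before surgery or the last date known alive. Separate bounds could give one death two dates. For a death recorded as UK/05/2020, a last visit on 20 April and last contact alive on 12 May, a visit-based bound would date the DFS event on 1 May, when the patient was known to be alive.
- Date a recurrence at the earliest possible date, but not before surgery or the last recurrence-free visit preceding its first report, and not after the visit that first reported it or the date of death. Listing 16.2.3.11 has no visit date, and listing 16.2.1.2 does not clearly cover follow-up visits. If follow-up visit dates are unavailable, use surgery as the lower bound.
- Delete the negative-time exclusion for events.
- Keep earliest-date censoring only for incomplete last-alive dates of event-free patients, and correct *secured*.

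Apply this to every DFS and OS analysis reported, including the addendum. The cost is SAP wording and a few lines of code. DFS and OS may look slightly less favourable.

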5.1 Study Assessments

5.1.1 Tumor assessments

All tumor evaluation is performed according to RECIST (Response Evaluation Criteria In Solid Tumors, V. 1.1, 2009, see Appendix 2 – RECIST 1.1 and table below) using CT scan or MRI scan. The baseline tumor assessment must be recorded and measured within 28 days prior to treatment start. The imaging technique for baseline tumor measurement(s) may be either computed tomography (CT, including spiral CT) or MRI according to investigator's choice and local routine standard of care. However, the same imaging technique must be used for all consecutive tumor assessments of the same patient. Whenever possible the same personnel should perform the tumor image evaluation.

All lesions identified at screening have to be assessed at each scheduled tumor measurement. Patients with measurable lesions will be eligible for inclusion. Measurable lesions must have at least one diameter of 20 mm with conventional techniques and at least 10 mm with spiral CT scan. Where there are several lesions, assessment is based on the sum of the longest diameters of the individual target lesions. Lymph nodes with a short axis of \geq 15 mm are considered measurable and assessable as target lesions. The short axis measurement should be included in the

sum of lesions in calculation of tumor response. Nodes that shrink to < 10 mm short axis are considered normal. All other pathological nodes (those with short axis \ge 10 mm but < 15 mm) should be considered non-target lesions.

In cases where there is suspicion of progression before the next scheduled assessment, an unscheduled tumor assessment should be performed.

Response Criteria

Definitions of the criteria used to determine objective tumor response/ Evaluation of target lesions:

Complete response	Disappearance of all target lesions. Any pathological lymph nodes (whether target or non-target) must have reduction in short axis to < 10 mm.
Partial response	At least a 30% decrease in the sum of diameters of target lesions, taking as reference the baseline sum diameters.
Stable disease	Neither sufficient shrinkage to qualify for PR nor sufficient increase to qualify for PD, taking as reference the smallest sum diameters on study (this includes the baseline sum if that is the smallest on study).

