Progressive disease	At least a 20% increase in the sum of diameters of target lesions, taking as reference the smallest sum on study (this includes the baseline sum if that is the smallest on study). In addition to the relative increase of 20%, the sum must also demonstrate an absolute increase of at least 5 mm. In the absence to clinical deterioration, a validation scan shall be performed after 4 weeks. Treatment continuation is warranted if tumor growth ≤20% of SLD. If PD is confirmed, the date of the pervious scan is counted as time point for PD. or Appearance of one or more new lesion. Note that the appearance of a single new lesion also requires validation of progression by another scan after 4 weeks.

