1.3 Endpoints

- 1.3.1 Primary Endpoint
 - Frequency and severity of AEs including peri- and post-operative complications (grade 2-4 AEs according to NCI-CTCAE V4.03)
 - o number of patients treated in compliance with protocol
 - Tumor response evaluation

clinical response parameters:

- o response rates (Δ tumor size / lymph node size), according to RECIST 1.1 criteria
- Δ PET-activity (standardized uptake value [SUV]) (analysis of this end point is not covered in this SAP)
 Pathologic response parameters:
- Pathologic regression grading according to Junker criteria (see Appendix 3 of CSP)
- 1.3.2 Secondary Endpoints
 - disease free survival
 - overall survival

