5.3 Inferential Analysis

No statistical tests are performed due to the small sample size.

DFS and OS will be described by means of Kaplan-Meier method. Estimates of median DFS and OS rates for specific time points (at e.g. 12, 24 and 36 months) will be provided with the associated 95% confidence limits.

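### Δ tumor size is summarised only in mm, so it depends on baseline size and cannot be read against the protocol's percentage limits; adding percent change is a free improvement

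*SAP*

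**What the plan says.** Protocol 2.4 and SAP 1.3 place radiologic response in the primary endpoint. The parameter is the response rate, with the size change named in parentheses: Δ "tumor size / lymph node size), according to RECIST 1.1 criteria".

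Protocol 5.1.1 sets the limits. Partial response is "At least a 30% decrease in the sum of diameters of target lesions, taking as reference the baseline sum diameters". Progression on target lesions is "At least a 20% increase in the sum of diameters of target lesions, taking as reference the smallest sum on study", and in addition "the sum must also demonstrate an absolute increase of at least 5 mm". New lesions count separately.

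SAP 5.2 gives the continuous measure one scale: Δ "tumor size will be defined as the difference [mm] between" the current and the baseline sum on the eCRF response page. SAP 7.1.3 puts two items into Table 14.3.1, "Tumor Response at Pre-Surgery Visit": overall response and Δ tumor size. Tables 14.3.1 to 14.3.8 are for the PP population and are repeated for ITT as 14.3.9 to 14.3.16. Listing 16.2.3.2 shows the current sum, the baseline sum, Δ tumor size and the overall response for each patient. SAP 2.14, which records departures from the protocol, does not discuss the choice of scale.

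**The concern.** A difference in mm is the product of two things: how large the lesions were at baseline and by what fraction they changed. The protocol's limits concern only the fraction, apart from the 5 mm floor for progression. A mean, median or quartile of the mm differences therefore mixes baseline tumor burden with change on treatment, and a reader cannot place it relative to -30% or +20%.

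Baseline sums may differ widely. A single lesion is measurable from "at least 10 mm with spiral CT scan", and several lesions are added together. What is at stake is whether the only continuous radiologic summary in the plan can be interpreted on the scale that the endpoint itself cites.

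**Working it through.** **Plan's own figure.** The documents state no figure for Δ tumor size. The nearest one is in Protocol Table 3: a reported radiologic response of 10%, with an exact 95% interval at N=30 of 2.1 to 26.5%. The Clopper-Pearson interval for 3/30 is 2.11% to 26.53%, so it reproduces. It concerns the response rate, which this point does not touch.

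**Inputs.** The limits come from Protocol 5.1.1 and the mm definition from SAP 5.2. All lesion sums below are illustrative. Only the pre-surgery scan is scheduled after baseline, so the smallest prior sum is taken to be the baseline sum (an unscheduled scan could change that).

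**Formulas.** With baseline sum b and pre-surgery sum c:
- mm change d = c - b
- percent change r = 100 × (c - b) / b, so d = b × r / 100

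**Step 1: the mm change that corresponds to each limit.** Partial response needs d ≤ -0.30 × b. Progression needs d ≥ the larger of 5 mm and 0.20 × b.

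| b (mm) | Partial response limit (mm) | Progression limit (mm) |
|---|---|---|
| 20 | -6 | +5 |
| 50 | -15 | +10 |
| 100 | -30 | +20 |
| 120 | -36 | +24 |

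The same -15 mm is exactly -30% from 50 mm (partial response) and -15% from 100 mm (stable disease).

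**Step 2: reversal of order.**

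| b to c (mm) | d (mm) | r | Target-lesion category by size limits |
|---|---|---|---|
| 20 to 14 | -6 | -30.0% | partial response |
| 70 to 60 | -10 | -14.3% | stable |
| 25 to 30 | +5 | +20.0% | progression |
| 100 to 115 | +15 | +15.0% | stable |

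In each pair, the mm scale gives the larger change to the patient whom RECIST calls stable.

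**Step 3: what a mean in mm measures.** Since d = b × r / 100, the mean of d divided by the mean of b is a baseline-weighted average of the percent changes. For the first two patients, mean d = (-6 - 10)/2 = -8 mm and mean b = (20 + 70)/2 = 45 mm, giving -8/45 = -17.8%. The unweighted mean percent change is (-30.0 - 14.3)/2 = -22.1%. The larger tumor pulls the mm summary towards itself.

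**Step 4: how often the order reverses.** The documents give no distribution of lesion sums, so this rests on assumptions: a lognormal baseline sum with median 45 mm and log-SD 0.3 to 0.7, independent of a percent change with mean 0 to -10% and SD 20%. By simulation, mm and percent order about 5% to 12% of random patient pairs oppositely. About 2% to 10% of pairs made of one partial responder and one other patient are reversed on the mm scale.

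**The case against.** The strongest reply is that the relative criterion is already analysed. The named parameter is the response rate, and Table 14.3.1 shows overall response directly beside Δ tumor size. The patient going from 20 to 14 mm is counted there as a partial response and the one going from 70 to 60 mm as stable. That stands. A reader might infer from the mm definition that patients are misclassified or the response rate is biased; nothing in the documents supports this.

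A reader might also argue that the continuous change carries most of the radiologic information because the plan expects only about three responders in 30. The documents do not support that either. The 10% in Table 3 is reported reference data, footnoted to a neoadjuvant nivolumab study and used to show interval width at N=30. It is not a stated expectation for pembrolizumab.

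Further points stand in part. SAP 2.5 also reports the median, quartiles and range, so the pull of large tumors on the mean is not the whole summary, although every one of these statistics still depends on baseline size. SAP 5.3 says "No statistical tests are performed due to the small sample size", and neither the 80% feasibility criterion (Protocol 8.1) nor the stopping rule on unresectability (Protocol 5.4) uses Δ tumor size. The mm value is not meaningless, since the progression rule has a 5 mm component. Under the assumptions in Step 4, the two scales agree for most pairs. Percent change can be derived by hand from Listing 16.2.3.2; that shows the repair is easy, but it does not put a usable summary into the planned tables.

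**Conclusion.** The point holds as a gap in the descriptive summary. The only continuous radiologic measure is on a scale that depends on baseline size, cannot be set against the 30% and 20% limits, and can order individual patients opposite to RECIST. The first two follow from the definitions alone. The reversal is shown by arithmetic on illustrative sums, and its frequency (about 5% to 12% of pairs) rests on assumed distributions.

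The consequence is modest. The tabulated RECIST response is correct as planned, and no alpha, power, sample size or decision changes. In a plan without efficacy tests the summaries are the result, so the improvement is worth making, particularly as it costs almost nothing.

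**What to change.** - In SAP 5.2, define percent change = 100 × (pre-surgery sum - baseline sum) / baseline sum. This also fixes the sign, which the present wording leaves open. At least one measurable lesion is required at entry, so the denominator is positive for any patient who meets that criterion.
- Summarise percent change in Table 14.3.1 (PP) and its ITT repeat, Table 14.3.9, with the statistics of SAP 2.5.
- Add it as a column in Listing 16.2.3.2.
- Keep the mm difference as a supplement, since the progression rule has an absolute component.
- A by-patient waterfall figure is optional and a matter of presentation.

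The cost is one derived variable, a few rows in two tables and one listing column. Both sums are already on the eCRF, so no new data are needed.
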